6.3 Controls

The primary objective of this PK bridging study is safety and tolerability, and thus it is acceptable to avoid the use of placebo.

6.4 Total duration

76 weeks (part A through C) or until TOFA is considered no longer needed by the investigator, whichever is first.

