Cohort 2 subjects will be seen in weekly intervals during Part A.

Cohort 1 and 2 subjects with clinical remission of SLE-CL can enter Part B as early as week 4 post baseline. Subjects who move from Part A to Part B prior to Week 8, will still be evaluated using the same visit schedule as subjects remaining in Part A until week 8.

Part B (week 8* – 24)

The primary objective of Part B is to assess safety and tolerability of TOFA, secondary objectives include effectiveness. Specifically, the PK of TOFA at the 5 mg dose based on Cohort 1 will be characterized.

- If CS are primarily given for SLE-CL, then CS may be decreased for clinically significant improvement as defined by a *Cutaneous Lupus Erythematosus Disease Area and Severity Index (CLASI)* activity score by $\geq 50\%$ from baseline and must be tapered for CLASI activity scores of 0 for > 2 months.

* Roll-over subjects in SLE-CL clinical remission may enter Part B as early as week 4

- If CS are mainly prescribed for other SLE manifestations besides SLE-CL, then CS can be decreased as per the investigator's decision, based on clinically significant findings of improvement.
- If the subject has been discontinued from CS and continues to be in SLE-CL clinical remission (CLASI activity score = 0), then the subject can enter Part C.

Subjects who move from Parts B to Part C prior to Week 24 will still be seen using the same visit schedule as subjects remaining in Part B until week 24.

Part C (week 24[†] – 76)

During Part C all therapies can be altered, per investigator discretion, with the exception of TOFA. The TOFA dose will remain stable throughout the study. Subjects who exit Part A or B early due to SLE-CL improvement will remain in Part C until they have been in the study for a total of 76 weeks.

4. Study description

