7.1 Evaluations for ALL Subjects

PART A

Cohort 1: Subject will be monitored at Day 1 and Day 5 of week 1, and then once per week during weeks 2, 3, 4, 5, 6, 7, 8.
PK samples will be drawn on Day 5 of Trial Week 1: pre-morning dose and 0.5, 1, 2, 4 and 8 hours post-morning dose of Day 5.

Cohort 2: TD1, and then once per week during weeks 2, 3, 4, 5, 6, 7, and 8.

PART B[‡]

Subjects of Cohorts 1 and 2 will be monitored at study visits at weeks 10, 12, 16, 20 and 24. CS dosing can be changed during Part B.

PART C[§]

Subjects of Cohorts 1 and 2 will be monitored at study visits every 8 weeks until week 76. Background medications, CS and other background medications can be changed during Part C, while TOFA remains stable.

Follow-up Period

All subjects who discontinue TOFA treatment at any time post-baseline will have a follow up phone call 10 weeks after the last TOFA dose to monitor for the development of safety events.

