8.3 Effectiveness Analyses

Due to the small sample size, results may not show statistical significance. Statistical significance may not be reached in final data analysis. However, a trend towards improved clinical status may assist planning efforts of a larger clinical trial to assess efficacy.

The efficacy population will be all subjects who were enrolled in the study and received at least 1 dose of TOFA. No interim analyses are planned. We will perform intention-to-treat analyses, with the last observation carried forward in primary analyses; and will also perform analyses on observed data in secondary analyses. As this is an open-label study, no control group is available. Efficacy measures are listed under Section 7. Data of subjects who enter Part B before week 8 and/or Part C before week 24 will be

considered on a last-observation (LOC) carried forward basis for endpoints of Part A and B, respectively.

To assess the benefits of TOFA on skin manifestations of SLE, we will use descriptive analysis and contingency table analysis, using Chi-square and Fisher Exact test as appropriate, to determine the proportion of subjects who are partial or complete CLASI responders at weeks 4, 8 and 24 compared to baseline. To assess the effect of TOFA on skin damage, we will compare the change (increase) of CLASI damage score¹⁶ from baseline to the end of Part B and C, respectively, using paired T-tests.

To assess the steroid –sparing properties of TOFA, we will determine the proportion of study subjects who can discontinue steroids at the end of Part B and C, respectively. We will also evaluate steroid sparing properties of TOFA for SLE-CL by comparing steroid doses (absolute and weight-adjusted) at baseline with those in the end of Part B and C, using a paired T-test.

Similarly, we will assess TOFA effect of overall disease activity in SLE as measured by the numeric SLEDAI and BILAG scores, respectively. We will also perform sub-analyses and evaluate improvement or resolution of other organ-system activity (e.g. serological activity – measured by anti-dsDNA antibodies and low complement levels; joint counts) using paired T-tests and contingency table analysis, as appropriate. In a similar fashion the change of the other SLE core response variables (CRV) besides disease activity (SLEDAI, BILAG) will be assessed at each study visit.

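### Section 6.4 lets the investigator end tofacitinib before week 76, in conflict with Section 3, and the plan does not say how skin relapse is observed or analysed after such a stop

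*Combined protocol and SAP*

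**What the plan says.** Section 6.4 (Total duration) gives the duration as "76 weeks (part A through C) or until TOFA is considered no longer needed by the investigator, whichever is first". It states no criterion, no earliest time and no link to the CLASI score.

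The Part C paragraph of Section 3 says: "During Part C all therapies can be altered, per investigator discretion, with the exception of TOFA". It adds: "The TOFA dose will remain stable throughout the study". Subjects who leave Part A or B early because their skin disease improved "will remain in Part C until they have been in the study for a total of 76 weeks". Sections 2, 6 and 7.1, and part B of Appendix 3, also describe tofacitinib as stable in Part C, but they do not repeat the 76-week statement.

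For follow-up after stopping, Section 7.1 says: "All subjects who discontinue TOFA treatment at any time post-baseline will have a follow up phone call 10 weeks after the last TOFA dose", and the purpose of the call is "to monitor for the development of safety events". Section 6.5 adds a request for a final visit at withdrawal, where applicable.

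Section 8.3 specifies intention-to-treat analyses "with the last observation carried forward in primary analyses", with observed-data analyses as secondary. Section 4.2 defines cutaneous relapse as a new CLASI activity score of at least 4 after complete response. Section 4.3 lists relapse, steroid dose and steroid discontinuation as exploratory endpoints for Parts B and C, with readings that include weeks 52 and 76.

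**The concern.** Two matters are linked. First, the protocol gives two answers to whether an investigator may end tofacitinib in Part C because it is judged unnecessary, so the regimen that the Part C results describe is not fixed.

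Second, if such stops occur, the plan does not say that skin and steroid assessments continue. Relapse can only be established by a later CLASI examination. A subject in remission who stops and is not examined again has a last score of 0, and LOCF keeps that score to week 76. Any error from this runs in one direction: an unseen relapse in that subject can only count as no relapse. Relapse and steroid sparing in Part C would then look more durable than they were. Section 8.3 says that trends may help to plan a larger trial, so these figures may be used even though they are exploratory.

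**Working it through.** The plan has no figure to reproduce: Appendix 3 (Sample size) says that no formal estimation was done. The check is a comparison of texts, followed by an illustration.

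**1. Do Sections 6.4 and 3 conflict?** Section 6.4 makes continuation depend on the investigator's judgement. Section 3 removes tofacitinib from what the investigator may alter in Part C and sets a total of 76 weeks for early improvers. If stable meant only that the dose does not change while on drug, the general statements of stability would fit Section 6.4. The exclusion of tofacitinib from discretionary changes and the 76-week statement would still not fit.

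**2. What is observed after a stop?** Section 7.1 schedules Part C visits every 8 weeks to week 76. Counting from week 24, these fall at weeks 32, 40, 48, 56, 64 and 72, plus week 76. If visits end with treatment:
- a stop at week 32 loses 6 CLASI assessments (weeks 40, 48, 56, 64, 72, 76);
- a stop at week 48 loses 4 (weeks 56, 64, 72, 76).

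The assured contact is a phone call about safety, which yields no CLASI score. A final visit may add one score at the time of the stop.

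**3. How would the subject be analysed?** Under LOCF, a last CLASI of 0 gives 0 at weeks 52 and 76, and the last steroid dose is carried in the same way. The observed-data analysis leaves the subject missing. It shows relapse among those still observed and does not recover relapses in those who stopped.

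**4. Illustration of size.** All inputs here are assumptions; the documents give none. Among subjects with complete response, let *s* be the fraction stopped before relapse and *r* the relapse risk to week 76, equal in stopped and continuing subjects. With full follow-up the proportion is *r*. With LOCF it is *r*(1 − *s*).

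| *r* | *s* | Reported *r*(1 − *s*) | Understatement *rs* |
|---|---|---|---|
| 25% | 25% | 0.25 × 0.75 = 18.75% | 6.25 points |
| 25% | 50% | 0.25 × 0.50 = 12.5% | 12.5 points |
| 50% | 25% | 0.50 × 0.75 = 37.5% | 12.5 points |
| 50% | 50% | 0.50 × 0.50 = 25% | 25 points |

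If stopped subjects have their own risk *r*ₛ, the understatement is *s* × *r*ₛ. It shrinks if they are the more stable subjects and grows if relapse is more frequent off drug.

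**5. Bounds without a common risk.** Suppose 10 subjects reach complete response, 1 relapse is seen and 4 stop in remission. LOCF reports 1/10 = 10%. The value with full follow-up could be anywhere from 1/10 = 10% to (1 + 4)/10 = 50%.

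**The case against.** The strongest reply is that much of the concern is inference.

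- No sentence says that visits end when tofacitinib ends, or that the phone call replaces them. The 76-week statement in Section 3 could be read as keeping such subjects in the study. Section 6.5 asks for every effort to document outcome, Appendix 3 (Risks) mentions follow-up safety visits, and the schedule includes an end-of-study visit. This stands: follow-up is unclear, not shown to be absent. None of these provisions assures serial CLASI scores.
- Section 8.3 does not mention the relapse endpoint or its denominator, and the specific carry-forward sentence for early roll-over concerns Parts A and B. This also stands. Applying LOCF to relapse follows from the general rule, not from an explicit instruction.
- Section 6.4 does not restrict the stop to remission. Remission is the natural case, but a partial responder could be stopped too and would be carried forward as a partial responder.
- The 76-week statement appears only in Section 3 and covers only early improvers.
- Primary endpoints are Day 5 pharmacokinetics and week 24 safety, and CLASI response is assessed to week 24. The study has 20 subjects, has no control group and disclaims significance. This limits the weight of the point.

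A reader might also infer that the two sites will run different regimens. The documents do not show this: one principal investigator monitors the database of both. The text permits divergence but does not predict it.

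**Conclusion.** The conflict between Sections 6.4 and 3 is explicit and needs one rule for both sites. The consequence for the analysis is conditional. It arises only if stops under Section 6.4 occur, scheduled CLASI and steroid assessments then lapse, and the general LOCF rule is applied to relapse.

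Under those conditions the reported relapse proportion can only be too low relative to full follow-up, and steroid results at weeks 52 and 76 would miss any later restart or increase. The range of 12.5% to 37.5% reported, against an assumed 25% to 50%, rests on equal risk in stopped and continuing remitters and on assumed stopping fractions. It is not an estimate for this trial.

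A reader might conclude that the plan scores stopped remitters as lasting successes, or that durability will be overstated by a known amount. The documents support neither: the end of visits and the scoring of relapse are not stated, and no relapse or stopping rate is given.

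The affected Part C endpoints are exploratory. The pharmacokinetic endpoint is untouched, and week 24 endpoints are affected only by stops before week 24, which Section 6.4 does not rule out. Severity: minor to moderate.

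**What to change.** Reconcile Section 6.4 with Section 3 so that a single rule on ending tofacitinib before week 76 applies at both sites. The choice of rule is a clinical matter for the sponsor and investigators.

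If the Section 6.4 option stays:
1. Record a stop on this ground as its own category. Section 6.5 already has the investigator ask the reason for withdrawal, so this is a small addition.
2. State that these subjects keep the scheduled CLASI and steroid-dose visits to week 76.
3. State that absence of relapse is not imputed by LOCF after such a stop.
4. Report relapse from all observed visits regardless of tofacitinib status, with on-drug and post-stop relapse shown separately.
5. Label any on-drug rate censored at the last dose as descriptive, because the decision to stop may be related to relapse risk.

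The cost is wording in the protocol and analysis section, a few off-drug visits that are already in the schedule, and a relapse figure that may be less favourable.

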6.5 Rescue clause, treatment failure & subject withdrawal

A subject will be considered a treatment failure and discontinued from the study if he/she experiences one or more of the following:

- Serious adverse event that is possibly related to TOFA;
- Important worsening of renal disease defined as a persistent increase in proteinuria as measured by the protein: creatinine (PC) ratio to values > 2.0 after achieving complete response of lupus nephritis, or doubling of proteinuria with values PC ratio > 3.0 after achieving a partial response of lupus nephritis;
- Need to increase current or initiation of new SLE background therapy due to non-renal SLE manifestations;
- Life-threatening SLE complications as judged by the investigator;
- Need for more than the protocol defined allowable CS rescue therapy as determined by the treating physician;
- No improvement of SLE-CL as measured by the CLASI by week 8;
- Two sequential absolute lymphocyte counts less than $< 0.5 \times 10^9$ or 500 cells/mm³;
- Two sequential hemoglobin values < 8.0 g/dL (80 g/L) or decreases greater than 2 g/dL on treatment;
- Female subjects that become pregnant during the study will discontinue study treatment. They will be continued to be followed in accordance as outlined in section **7.3.10**.

Subject Withdrawal

Subjects may withdraw from the study at any time at their own/their legal guardian's request, or they may be withdrawn at any time at the discretion of the physician investigators for safety, behavioral, or administrative reasons. If a subject does not return for a scheduled visit, every effort should be made to contact the subject. In any circumstance, every effort should be made to document subject outcome, if possible.

The investigator will inquire about the reason for withdrawal, request the subject to return all unused investigational product, request the subject to return for a final visit, if applicable, and follow-up with the subject regarding any unresolved AEs.

7 If the subject withdraws from the study, and also withdraws consent for disclosure of future information, no further evaluations should be performed, and no additional data should be collected. The sponsor may retain and continue to use any data collected before such withdrawal of consent. Planned Assessments & Evaluations

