6.2 Dosing

TOFA dosing: Twice daily orally

As documented in the TOFA Investigator brochure (Section 6.1; Version March 2016) doses up to 30 mg twice daily were safe and tolerated. However, for the purpose of this study only the dose of TOFA approved for rheumatoid arthritis (5 mg PO BID) will be tested.

Based on TOFA PK in the Rheumatoid Arthritis (RA) population [body weight (BW) ranging from 40 kg - 140 kg)], clearance (CL) of TOFA is not dependent on body weight in adult subjects. Thus, the starting dose of TOFA will be 5 mg orally twice daily, an approved dose of TOFA in adult RA subjects in most countries. Dose escalation will not occur even with lack of SLE-CL improvement.

Corticosteroids (CS):

At study entry, CS dosage must be \leq 20mg/day. CS should be kept stable up to and including week 4.

CS can be decreased starting week 5:

- CS may be decreased for improvement of the CLASI activity score by \geq 50% from baseline and must be tapered for CLASI activity scores of 0 for $>$ 8 weeks (or 2 subsequent study visits, whatever is shorter), provided CS are mainly prescribed for SLE-CL. This will minimize morbidity associated with CS use as much as possible.
- If CS are mainly prescribed for other SLE manifestations besides SLE-CL, then CS can be decreased as per the investigator's decision, even in the setting of complete response of SLE-CL, based on continued improvement of clinical findings of SLE.

Oral CS may be increased above the baseline level up to max of 60 mg/day for new BILAG A or B flares in organ systems other than mucocutaneous organ system (i.e. neurologic, ophthalmologic, musculoskeletal, cardiopulmonary, gastrointestinal, renal, hematological organ systems) but must be returned to baseline dose or lower within 14 days. If this is not achieved then the subject is considered a treatment failure.

- Up to 3 doses of pulse methylprednisolone may be given for new BILAG A or B flares instead.
- CS increases can occur no more than 3 times during the duration of the study, Part A- C.
- Subjects requiring more than 3 CS increases will be withdrawn from treatment phase of study.

Other anti-inflammatory medications used as part of standard of care (SOC) for SLE

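### Read literally, the third exit criterion in section 6.5 discontinues a subject for a corticosteroid rescue that section 6.2 allows

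*Combined protocol and SAP*

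**What the plan says.** **Section 6.2 (Dosing, corticosteroids)** gives a rescue allowance. "Oral CS may be increased above the baseline level up to max of 60 mg/day for new BILAG A or B flares" outside the mucocutaneous system. Seven organ systems are named, and renal is one of them. The dose "must be returned to baseline dose or lower within 14 days"; otherwise the subject is a treatment failure. Up to three pulse doses of methylprednisolone may be given instead. "CS increases can occur no more than 3 times during the duration of the study", counted over Parts A to C, and "Subjects requiring more than 3 CS increases will be withdrawn from treatment phase of study".

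**Section 6.5 (Rescue clause)** opens with a rule that any single listed event means treatment failure and discontinuation from the study. Two items matter here:

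- Third item: "Need to increase current or initiation of new SLE background therapy due to non-renal SLE manifestations".
- Fifth item: "Need for more than the protocol defined allowable CS rescue therapy as determined by the treating physician".

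Appendix 3 repeats both items in parts H and M, in nearly the same words. None of the three places exempts the 6.2 rescue from the third item.

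**Whether CS is background therapy.** Section 6.1 lists oral CS under allowable background SLE therapy. Section 3 (Part A) includes CS among the background medications. Section 7.1 (Part C) and section 8.2 use the term in the same way. Usage is not fully uniform: in 6.2, the paragraph on other anti-inflammatory drugs speaks of background therapy after a list that leaves CS out.

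**The concern.** The two sections give opposite instructions for the same event. Under 6.2, a subject whose CS is raised for, say, a musculoskeletal flare and tapered within 14 days stays in the trial. Under the third item of 6.5, the same subject needed more background therapy for non-renal SLE and must leave.

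The week-24 primary endpoint in section 4.1 consists of adverse events and laboratory abnormalities. Hematology and chemistry come from scheduled visits, and section 7.3.2 records adverse events on the CRF through the last subject visit. A literal exit would shorten that observation for a subject the dosing section meant to keep on drug. It would also raise the treatment-failure count and the amount of week-24 CLASI data carried forward under section 8.3. There are two sites, and they could resolve the conflict differently.

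**Working it through.** The plan states no sample-size or power figure that depends on this point, so there is none to reproduce. The check is a comparison of texts, followed by simple counts.

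**1. Does the third item reach the 6.2 rescue?**

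| Question | Section 6.2 | Section 6.5, third item, with copies |
|---|---|---|
| Trigger | New BILAG A or B flare, non-mucocutaneous | Non-renal SLE manifestation |
| Action | CS raised, or pulse given | Background therapy raised or newly started |
| Consequence within limits | Subject stays | Treatment failure, discontinued |
| Consequence beyond limits | Failure or withdrawal | Treatment failure, discontinued |

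Of the seven organ systems in 6.2, 7 − 1 = 6 are non-renal. The overlap therefore covers six of the seven systems.

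**2. Subjects not on CS at baseline.** Section 3 expects up to 80% on CS, so at least 20 × (1 − 0.80) = 4 of 20 would not be. For them a rescue is newly started CS, which falls under the initiation limb of the third item. It is also less clear that the 6.2 wording, an increase above baseline, covers them.

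**3. Does the fifth item act as an exception?** It makes CS beyond the allowance a failure. It is a further trigger in a list where one trigger suffices, and it does not limit the third item. Under the literal reading it still has a use, for excess CS given for renal flares.

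**4. When does the conflict stand alone?** Part B is the cleanest case, because section 7.1 lets CS dosing change there. In Part A other rules intervene: "CS should be kept stable up to and including week 4", and section 3 keeps CS unchanged for the whole part. In Part C, section 3 frees all therapies except tofacitinib, which is a separate tension with the third item.

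**5. Loss per affected subject, by example.** Part B visits (section 7.1) are at weeks 10, 12, 16, 20 and 24.

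| Exit at | Visits lost | Net, if a later final visit replaces one | Weeks lost |
|---|---|---|---|
| Week 10 | 12, 16, 20, 24 = 4 | 3 | 24 − 10 = 14 |
| Week 16 | 20, 24 = 2 | 1 | 24 − 16 = 8 |

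As a share of planned follow-up if all 20 subjects reached week 24:

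- To week 24: 20 × 24 = 480 subject-weeks; 14/480 = 2.9% and 8/480 = 1.7%.
- Part B only: 20 × (24 − 8) = 320 subject-weeks; 14/320 = 4.4% and 8/320 = 2.5%.

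These denominators are maxima, because section 6.5 also removes subjects with no skin improvement by week 8.

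**6. How many subjects?** The documents give no flare rate and no share of flares tapered in time. For scale only, let *p* be an assumed share of subjects needing one within-limit rescue for such a flare, with subjects independent. Expected exits are 20*p*, and the chance of at least one is 1 − (1 − *p*)^20.

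| Assumed *p* | Expected exits | Chance of at least one |
|---|---|---|
| 5% | 1 | 0.6415 |
| 10% | 2 | 0.8784 |
| 20% | 4 | 0.9885 |
| 30% | 6 | 0.9992 |

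Nothing in the documents supports one row over another.

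**The case against.** The best reply is that the list can be read coherently. Section 6.5 uses two terms, background therapy in the third item and CS rescue in the fifth, and the fifth makes only an excess a failure. Section 6.2 gives the specific CS rule and deals with other drugs under its own heading. A short burst returned to baseline can be seen as rescue and not as an increase in background therapy. The literal reading would also cancel most of the 6.2 allowance. This is probably what was intended. It remains an inference, though: four places class CS as background therapy, and no text says which section prevails. A mandatory exit rule should not rest on inference.

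The reply is stronger on consequences, and most of it stands:

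- Section 8.2 keeps everyone with at least one dose in the safety population, so data before exit count.
- Observation does not stop at exit. Section 6.5 asks staff to "request the subject to return for a final visit, if applicable, and follow-up with the subject regarding any unresolved AEs". Section 7.3.2 continues SAE reporting for 28 days after the last dose. Section 2 provides a 10-week follow-up period, described in 7.1 as a phone call. Appendix 3 L also mentions follow-up safety visits, without giving their content. After exit at week 16 the call falls at about week 26, beyond the endpoint; after exit at week 10 it falls at about week 20. The clear loss is in scheduled laboratory, AE and CLASI visits.
- One principal investigator reviews all safety events and monitors both sites' databases, which limits divergence between sites.

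A reader might infer that the conflict biases the week-24 skin response. The documents do not support that: the flares concerned are outside the mucocutaneous system, so a carried-forward CLASI score need not be wrong, and section 8.3 adds an observed-data analysis. Nor is the PK endpoint touched in the Part B case, since it is measured on Day 5.

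**Conclusion.** The conflict is real and lies in the wording. Section 6.2 retains a subject given CS rescue within its limits for a non-renal, non-mucocutaneous BILAG A or B flare, while the third item of 6.5 and both Appendix 3 copies, taken literally, discontinue that subject. This is more than a missing detail: two stated rules contradict each other, although the probable intent can be guessed.

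The size is modest and partly unknown. Each affected subject would stop tofacitinib and lose scheduled visits to week 24, four visits and 14 weeks or two visits and 8 weeks in the two examples. The number of such subjects cannot be computed from the documents. The conclusion rests on reading CS as background therapy, which the protocol's own usage mostly supports, and on a site applying the third item as written.

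A reader might go further and conclude that the safety endpoint fails or that affected subjects leave the analysis. Neither follows, because data before exit are kept and some follow-up continues.

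**What to change.** In the third item of section 6.5, and in its copies in Appendix 3 H and M, add: 'other than CS rescue (oral or pulse, including newly started CS) within the limits of Section 6.2'. Naming pulse and newly started CS matters, because a bare reference to CS increases does not clearly cover methylprednisolone pulses or subjects who were not on CS at baseline.

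The cost is one phrase at three places, with no new data, visit or analysis. If the probable intent is the true one, the phrase only states it.

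Section 6.2 withdraws subjects from the treatment phase, whereas 6.5 discontinues them from the study. It may be tempting to harmonise these terms in the same edit, but they should be left alone here: the choice may change which visits continue after tofacitinib stops, so it is a separate design decision.
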